#### A2.2 Extension to allow for cross-reactivity

We now suppose a situation in which a sample is found ZIKV IgM+ and DENV IgM+.

In the previous example it was necessary to sum over all the possible times  $u, -2 \le u \le G_i$  when the ZIKV infection might have occurred. To take the possibility of a DENV infection into account, this becomes a two-dimensional problem, in which we must consider all the possible times  $u, w, -2 \le u \le G_i, -2 \le w \le G_i$  when either infection might have occurred.

$$\begin{split} & p\left(Z + D +_{20} \mid I_{Z,-2:20}\right).p\left(I_{Z,-2:20}\right) \\ & \frac{p\left(Z + D +_{20} \mid I_{Z,-2:20}\right).p\left(I_{Z,-2:20}\right)}{p\left(Z + D +_{20} \mid I_{Z,-2:20}\right).p\left(I_{Z,-2:20}\right).p\left(I_{D,-2:20}\right)$$

This formula refers to the sensitivity of the ZIKV IgM and its cross reactivity to DENV IgM, and makes some simplifying approximations regarding the co-occurrence of ZIKV and DENV. The specificity term is the probability of obtaining a Z+D+ result in the absence of a recent infection by either ZIKV or DENV.

45

Author: [name] (UNIVBRIS)

#### A2.3. Extensions to sequences of tests.

In principle, calculations of this sort can be extended straightforwardly to sequences of tests, although they become increasingly tedious. The way in which the sensitivity and specificity of the entire testing algorithm and will be calculated and applied to sequences of tests remains to be determined, so we will not develop the statistical framework further here.

# APPENDIX 3. Sources of data on persistence of PCR, IgM tests, IgG rising titer

Study	ZIKV, DENV, CHIKV	PCR	IgM	IgG rising titer
Paz-Bailey NEJM 2017 [10]	ZIKV	Triplex RT-PCR		
etc				
etc				

# APPENDIX 4. Sources of data Sensitivity, Specificity, Cross-reactivity of diagnostic tests

Study	PCR, IgG	IgM,	ZIKV, CHIKV	DENV,	Sensitivity	Specificity	Cross- reactivity

46

Author: [name] (UNIVBRIS)

## APPENDIX 5. Role of Antibody persistence in diagnosis of congenital infection

The criteria for congenital infection (CI) are: PCR+ in serum, urine or CSF OR IgM+ in serum, urine or CSF; OR congenital zika syndrome meeting an agreed definition (see *Section 5.2*) Infants who lose IgG antibody, or who have consistently falling IgG titers, will be regarded as not CI.

The remaining children are those that remain IgG+ at last follow up. They have a probability of being congenitally infected that increases with time, but it is necessary to take into account that they may have acquired antibody following a post-natal infection.

Suppose we have available information on the probability Ab(t) that an uninfected child born to an antibody +ve mother remains IgG+ t weeks after delivery. Suppose also that we have information on the probability Pn(t) that an initially IgG- newborn is IgG+ t weeks after birth as a result of a postnatal infection.

Now consider the babies born to women infected in pregnancy: all will be initially lgG+. The proportion lgG+ at time t is:

$$X(t) = (V + (1-V)Ab(t)) + (1-V-(1-V)Ab(t))Pn(t)$$

If there was no post-natal acquisition of antibody, we should observe X(t) fall off to an asymptote V representing the vertical transmission rate. Instead we expect X(t) to fall until all maternal antibody is lost, and then continue to rise in response to postnatal acquisition. As we can observe Ab(t) and X(t), and we have data on and Pn(t), we can recover an estimate of V.

If AB(t) indicates having IgG antibody at time t, then the probability that a child who is IgG+ at age t is CI is:

$$p(CI \mid AB(t)) = \frac{p(AB(t) \mid CI).p(CI)}{p(AB(t) \mid CI).p(CI) + p(AB(t) \mid \overline{CI}).p(\overline{CI})}$$
$$= \frac{V}{V + (1 - Ab(t))V}$$

These analyses can be extended to include covariates, and can be integrated into the calculation of the vertical transmission rate (Section 7.1) [14].

Data on Ab(t) will be generated from within ZIKA-VT, but we will also refer to other sources of information as listed in the following table, which will be updated regularly:

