#### 5.2 Numerator for VTR

Fetuses will be regarded as vertically infected if fetal or placental tissue, or amniotic fluid, tests PCR+. Children will be regarded as vertically infected on the basis of IgM or PCR evidence within 7 days of delivery. Infants who lose antibody will be regarded as not vertically infected: this includes infants in whom a falling IgG titer is observed as well as those who become IgG-.

There are reports of children with clinical signs of congenital infection, such as microcephaly, whose mothers were infected in pregnancy, but in whom no laboratory evidence of congenital ZIKV can be obtained from testing serum and CSF for IgM and PCR. Definitions of congenital zika in the absence of laboratory evidence are being developed [2, 3], which may be revised as new data becomes available. Although the evidence is not clear at the time of writing, it seems likely that these infected children will remain IgG antibody positive.

Infants who are IgG antibody positive when last seen may be congenitally infected. The probability that they are congenitally infected depends on two factors: firstly, their age, because maternal antibody declines over time and is usually absent within 15 months. Secondly, the risk of post-natal

Author: [name] (UNIVBRIS)

15

infection. Appendix 5 describes statistical analyses that use data on antibody loss in control children born to IgG+ mothers, and data on post-natal infection on initially IgG- newborns, to estimate the probability of vertical infection in all IgG+ infants whose infection status cannot otherwise be determined.

It remains possible either that congenital infection can take place, causing damage, and clearing prior to delivery and leaving no laboratory markers; or that maternal infection affects fetal development without crossing the placenta. It is for this reason that ZIKA-VT includes a 2nd control group, of children born to mothers with no infection in pregnancy.

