#### 7.2 Risk of severe outcomes of congenital infection

A similar form of analysis will be carried out for severe outcomes of congenital infection. The precise definition remains to be determined, but could include: fetal death, stillbirth, microcephaly, cranial disproportion, or ZIKV-related death within the first two years. The analysis will estimate the risk of severe outcomes conditional on vertical transmission having taken place. This clarifies that there may be two distinct processes: risk factors for congenital infection, and risk factors for severe damage given congenital infection.

The form of analysis for severe clinical outcomes conditional on vertical infection parallels that for vertical transmission rate. Here,  $c_i$  is the risk of severe outcomes in a child born to women i, and C(t) is the probability of severe outcomes given maternal infection in week t. Data  $Z_i=0,1$  indicating severe (1) or non-severe (0) outcomes is a Bernoulli realization of  $c_i$ , and can be used to update C(t) and  $\pi_i(t)$ :

$$c_i = \sum_t C(t)\pi_i(t), \quad Z_i \sim Bern(c_i)$$

Author: [name] (UNIVBRIS)

19

The analysis can be extended to include risk factors as shown above.

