## 7.3 Severe outcomes with no laboratory evidence of in utero transmission

As noted in Section 5, this may possibly represent a distinct outcome, requiring its own analysis with respect to GA at infection and other risk factors. If so, the analysis would be along the same lines as the analyses above. Alternatively, if, as we suspect, persistent antibody is found in these cases, then no special provision is required.

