#### **TABLES**

#### Table 1: Risks of Vertical Transmission and Congenital malformation.

#### **Definitions:**

- 1. Presumed maternal infection based on PCR+, IgM+, Seroconversion or rising IgG titer
- 2. Trimester, most likely trimester based on test dates and persistence
- 3. Vertical infection based on IgM+, PCR+ in cord or sample from newborn < 7days old, or persistent antibody.
- 4. Severe and mild congenital malformation, to be defined

	Trimester of presumed infection	Symptoms during pregnancy	Number of Mothers infected	Number Vertically infected	Number of Congenital malformations (severe)	Number of Congenital malformations (mild)
	1	Yes				
		No				
ZIKV	2	Yes				
		No				
	3	Yes				
		No				
	1	Yes				
		No				
DENV	2	Yes				
		No				
	3	Yes				
		No				
	1	Yes				
		No				
CHIKV	2	Yes				
		No				
	3	Yes				
		No				

Author: [name] (UNIVBRIS)

34

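### SAP Appendix 5 lets the clinical syndrome alone count as congenital infection, which conflicts with Sections 5.2 and 10.2 and, if carried into Section 7.2, makes severe risk given infection partly circular

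*SAP*

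**What the plan says.** SAP Section 5.2 sets out the numerator of the vertical transmission rate (VTR). "Fetuses will be regarded as vertically infected if fetal or placental tissue, or amniotic fluid, tests PCR"-positive. For live births, "Children will be regarded as vertically infected on the basis of IgM or PCR evidence within 7 days of delivery". Infants who lose antibody, or whose titre falls, count as not infected. "Infants who are IgG antibody positive when last seen may be congenitally infected", and Appendix 5 is to supply the probability. For children with clinical signs such as microcephaly but no laboratory evidence, Section 5.2 reports that definitions are under development and thinks persistent IgG likely. It does not adopt a clinical definition as a numerator criterion. It also allows that maternal infection might harm the fetus without transmission, and gives this as a reason for the second control group.

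Table 1 uses: "Vertical infection based on IgM+, PCR+ in cord or sample from newborn < 7days old, or persistent antibody". Section 10.2 assigns each child a status from test results: 0, 1, or a probability that depends on antibody persistence.

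Appendix 5 gives the criteria as "PCR+ in serum, urine or CSF OR IgM+ in serum, urine or CSF", then "OR congenital zika syndrome meeting an agreed definition", with a cross-reference to Section 5.2. Its next sentence excludes infants who lose IgG or have consistently falling titres.

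On outcomes, Section 7.2 states: "The analysis will estimate the risk of severe outcomes conditional on vertical transmission having taken place". The severe outcome is still to be defined, but microcephaly and cranial disproportion are candidates. Of severe outcomes without laboratory evidence, Section 7.3 says "this may possibly represent a distinct outcome, requiring its own analysis with respect to GA at infection and other risk factors". Alternatively, if persistent antibody is found in them, it sees no need for special provision.

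**The concern.** Section 10.4 names VTR and the risk of serious outcomes given transmission as the two pre-specified outcomes. Both depend on who counts as vertically infected. Under Appendix 5 a child with the syndrome and no laboratory evidence counts as infected. If the same classification is used in Section 7.2, such a child joins the denominator because it has the outcome, and the estimated severe risk rises by construction.

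The same step takes that child out of the cohort with maternal infection but no vertical infection (MI-No VI). Section 2.1 asks for outcomes in the absence of in utero transmission, and that cohort is where damage without transmission would show.

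**Working it through.** **1. The rules side by side**

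| SAP place | Samples | Window | IgG at follow-up | Syndrome alone |
|---|---|---|---|---|
| 5.2 | Fetal or placental tissue, amniotic fluid (PCR); child's IgM or PCR | 7 days (child) | Lost: not infected. Still positive: probability | Not adopted |
| Table 1 | Cord or newborn IgM, PCR | Under 7 days | Persistent: infected | None |
| 10.2 | Test results, not itemised | Not stated | Probability | None |
| Appendix 5 | Serum, urine, CSF | Not stated | Lost: not infected. Still positive: probability | Sufficient |

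**2. One child traced through the rules.** Take a child who meets the syndrome definition, is PCR- and IgM-negative in the first week, and later loses IgG. Sections 5.2 and 10.2 and Table 1 give not infected. Appendix 5 gives infected by its criteria and not infected by its next sentence, with no order of precedence. The Appendix 5 model also has no place for this child: without postnatal infection its IgG-positive proportion falls to V, so every infected child is taken to keep IgG.

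**3. Effect on the two outcomes.** Let V be the laboratory-defined VTR, C the severe risk among those infected, and q the fraction of infected pregnancies with syndrome only, all counted as severe. V, C and q are assumptions, because the SAP gives none of them. Adding the syndrome-only children gives:

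- VTR: V becomes V + q
- Severe risk given infection: C becomes (VC + q)/(V + q)

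With q = 1%:

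| V | C | (VC + q)/(V + q) | Rise |
|---|---|---|---|
| 30% | 30% | (0.090 + 0.010)/0.31 = 32.3% | 2.3 points |
| 10% | 20% | (0.020 + 0.010)/0.11 = 27.3% | 7.3 points |
| 5% | 10% | (0.005 + 0.010)/0.06 = 25.0% | 15.0 points |

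With the approximately 1000 infected women of Section 10.3, the middle row is 20/100 = 20.0% (95% Wilson interval 13.3 to 28.9) against 30/110 = 27.3% (19.8 to 36.3), and VTR goes from 10% to 11%. At V = 10% and C = 20%, q = 2% gives 33.3% and q = 3% gives 38.5%.

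**4. If some of these children keep IgG.** Suppose a share r of them is counted as infected through persistent antibody anyway. The laboratory-based figure becomes (VC + rq)/(V + rq). With V = 10%, C = 20%, q = 1% and r = 0.5 (assumed), it is 0.025/0.105 = 23.8%, so the gap to 27.3% is 3.5 points. At r = 1 the gap is zero.

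**5. Effect on the MI-No VI cohort.** Under a laboratory definition these cases are q/(1 - V) of the cohort. At q = 1% that is 0.01/0.70 = 1.4%, 0.01/0.90 = 1.1% or 0.01/0.95 = 1.1% for the three values of V. Under Appendix 5 it is zero.

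**6. The antibody probability.** A laboratory definition would use the Appendix 5 probability that an IgG-positive child is infected. As printed, V/(V + (1 - Ab(t))V) = 1/(2 - Ab(t)). This does not depend on V, ignores postnatal infection Pn(t), and falls from 1 (Ab = 1) to 0.5 (Ab = 0) as maternal antibody disappears, although Appendix 5 says the probability increases with time. Bayes' rule with the appendix's own terms gives V/(V + (1 - V)[Ab(t) + (1 - Ab(t))Pn(t)]). The denominator is its X(t). With Pn = 0 this rises from V (Ab = 1) to 1 (Ab = 0).

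**The case against.** Several stronger readings are tempting, and the SAP does not support them.

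- A reader might infer three wholly incompatible definitions. Section 5.2 already uses IgG loss and persistence, and Table 1 is a declared basic output in which a yes/no antibody rule is a deliberate simplification. Appendix 5 refers back to Section 5.2, so its missing window may be an incomplete restatement. The substantive conflict is the clinical criterion.
- A reader might infer that Section 7.3 commits these children to a separate outcome. It is conditional, with reliance on persistent antibody as the alternative. Still, neither branch treats the syndrome alone as proof of transmission.
- A reader might infer that the Section 7.3 question becomes unanswerable. Individual test results stay on record and Table 2 lists all congenital anomalies, so the cases can be recovered. Severe outcomes that fall short of the syndrome definition stay in MI-No VI. The question is weakened, not lost.

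It is also fair to say that the syndrome and severe-outcome definitions are both open, and that Section 5 gives the Expert Group responsibility for the criteria. That leaves the extent of the overlap unknown. It does not reconcile passages that classify the same child differently, and a syndrome defined by signs that also serve as the outcome would be circular in Section 7.2 whatever its final wording.

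**Conclusion.** The point stands in this form: the clinical criterion in Appendix 5 contradicts Sections 5.2 and 10.2 and the exclusion sentence in Appendix 5 itself. If used for Section 7.2, it inflates severe risk given infection through the children admitted on the syndrome alone. The circularity is partial, and it is likely rather than certain because microcephaly is only an example sign in Section 5.2 and only a candidate outcome in Section 7.2.

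The size cannot be read from the SAP. The rises of about 2, 7 and 15 points assume that 1% of infected pregnancies are syndrome-only, that all of these are severe, and that none has persistent IgG. The SAP leans against the last assumption, so the true effect could be much smaller, down to none. The contradiction needs settling at any size, because it concerns both pre-specified outcomes.

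**What to change.** Use one laboratory-based definition of vertical infection for the main analyses in Sections 7.1 and 7.2. State it once and cite it from Section 5.2, Table 1, Section 10.2 and Appendix 5. It should comprise:

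- PCR-positive fetal or placental tissue or amniotic fluid, so that fetal deaths and stillbirths keep their route into the infected group;
- IgM or PCR in cord or child within the stated window;
- for children still IgG-positive when last seen, a probability of infection, entered as a latent or mixture status, because Y_i in Section 7.1 is 0/1 and cannot take a probability directly.

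Correct the Appendix 5 probability first, to V/(V + (1 - V)[Ab(t) + (1 - Ab(t))Pn(t)]).

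Keep syndrome without laboratory evidence as a separate category analysed under Section 7.3, and report the syndrome-inclusive definition as a labelled sensitivity analysis. The Expert Group should confirm the reconciled wording, including how a child with the syndrome who loses IgG is classified.

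The cost is SAP wording and one additional sensitivity analysis.

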#### 10.2 Missing data

With so many variables, and with so many different analyses, it is difficult to make any general comments on methods for handling missing data. The following comments set out our general approach:

1. In the case of diagnostic test variables, the concept of "missing data" is not applicable: for the purposes of determining whether mothers have been infected in pregnancy, and if so when, the methods are designed to deal with any pattern of test results occurring at any time before, during, and after pregnancy, including no tests at all. A probability distribution will be created for every woman reflecting when maternal infection took place and whether it took place. With regards to vertical infection, the analysis will assign every child a probability of being vertically

Author: [name] (UNIVBRIS)

31

infected, based on test results, which will be 0,1, or a probability determined by the duration of antibody persistence when last tested.

- 2. With regards to explanatory variables, all analyses will be based on a "complete data" analysis, which assumes that data is missing without regard to outcomes.
- 3. Loss to follow-up will be carefully monitored and tabulated in relation to infection status, in both pediatric and maternal follow-up studies.
- 4. For categorical pediatric outcomes, survival analyses will treat loss to follow-up as censored observations. Alongside these analyses, sensitivity to assumptions about informative censoring will be carried out, including examination of the most extreme assumptions, in which (a) all, or (b) no, censored observations are assumed to reach the endpoint

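### Appendix 5: the infection probability for leftover IgG+ infants uses the all-infant rate V as prior and ignores the PCR/IgM and titer results that define that group

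*SAP*

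**What the plan says.** Appendix 5 sorts the infants of infected mothers into three groups.

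- Infected (score 1): "PCR+ in serum, urine or CSF OR IgM+ in serum, urine or CSF", or an agreed syndrome definition.
- Not infected (score 0): "Infants who lose IgG antibody, or who have consistently falling IgG titers, will be regarded as not CI".
- Undetermined: "The remaining children are those that remain IgG+ at last follow up".

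V is introduced for a different population. The X(t) equation opens with "Now consider the babies born to women infected in pregnancy", that is, all of them, and without post-natal infection X(t) would "fall off to an asymptote V representing the vertical transmission rate". The Bayes expression for p(CI | AB(t)) follows. It conditions only on being IgG+ at age t, and the numerator of its closed form sets p(CI) = V and p(AB(t) | CI) = 1.

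Two other places put this probability to use. Section 5.2 says that Appendix 5 serves "to estimate the probability of vertical infection in all IgG+ infants whose infection status cannot otherwise be determined". Section 10.2, item 1, says that each child receives a value "which will be 0,1, or a probability determined by the duration of antibody persistence when last tested". Appendix 5 adds that the analyses can be integrated into the VTR calculation of Section 7.1.

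**The concern.** The prior and the group do not match. V describes all infants of infected mothers. The undetermined infants are what is left after two selections. The first removes infected infants who were PCR+ or IgM+, which lowers the chance of infection among those who remain. The second removes uninfected infants with falling titers, which raises it. A probability that conditions on IgG status alone reflects neither.

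For mothers, the SAP takes the opposite line: Section 7.6 asks that accuracy adjustments rest on the whole algorithm and on all results through the pregnancy. Appendix 5 does not do the same for infants.

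VTR is one of the two pre-specified outcomes in Section 10.4, and Section 7.1 needs an infection outcome for each child. A wrong child-level score would therefore enter the main estimate.

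**Working it through.** **Inputs.** The SAP gives no value for V, for Ab(t) (the share of uninfected infants still IgG+ at age t), or for s and f. All numbers below are assumptions: V = 0.20, s = 0.7, Ab = 0.2, f from 0 to 0.9, and post-natal infection Pn = 0. Also assumed: all infants are tested, there are no false-positive newborn results, and infected infants stay IgG+ without a falling titer.

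**1. The printed closed form.** V/(V + (1−Ab)V) = 1/(2−Ab). V cancels, Pn(t) is absent, and the value falls from 1 at Ab = 1 to 0.5 at Ab = 0, although the text says that the probability rises with time. Putting p(AB | CI) = 1, p(CI) = V and p(AB | not CI) = Ab into the SAP's own Bayes line gives instead

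p = V / (V + (1−V)Ab) = 0.20 / (0.20 + 0.16) = 0.556.

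(The printed form gives the same 0.556 here only because Ab happens to equal V.) The rest uses the corrected form.

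**2. True probability in the leftover group.** Infected infants left: V(1−s) = 0.06. Uninfected infants left: (1−V)Ab(1−f) = 0.16(1−f). The true share infected is 0.06 / (0.06 + 0.16(1−f)).

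**3. VTR implied by the scores.**

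Vs + [V(1−s) + (1−V)Ab(1−f)]·p = 0.14 + [0.06 + 0.16(1−f)] × 0.556

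| f | True probability | Assigned p | Implied VTR (true 20%) |
|---|---|---|---|
| 0 | 0.06/0.22 = 0.273 | 0.556 | 26.2% |
| 0.5 | 0.06/0.14 = 0.429 | 0.556 | 21.8% |
| 0.8 | 0.06/0.092 = 0.652 | 0.556 | 19.1% |
| 0.9 | 0.06/0.076 = 0.789 | 0.556 | 18.2% |

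**4. General form.** Since [V + (1−V)Ab]·p = V and (1−V)Ab·p = V(1−p), the bias is V(1−p)(s−f). Check at f = 0: 0.20 × 0.444 × 0.7 = 0.062. The sign changes at f = s.

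**5. Range at V = 20%, with s 0.5–0.9, Ab 0.05–0.5 and f 0–0.9.**
- Highest (s = 0.9, Ab = 0.5, f = 0): p = 0.20/0.60 = 0.333; 0.20 + 0.20 × 0.667 × 0.9 = 32.0%.
- Lowest (s = 0.5, Ab = 0.5, f = 0.9): 0.20 + 0.20 × 0.667 × (−0.4) = 14.7%.

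**6. Late follow-up.** With s = 0.7 and f = 0, VTR is 22.3% at Ab = 0.05, 21.0% at Ab = 0.02 and 20.0% at Ab = 0. Post-natal infection brings the bias back: Ab is then replaced by q = Ab + (1−Ab)Pn. With V = 0.10, s = 0.5, f = 0, Ab = 0 and Pn = 0.10, p = 0.10/(0.10 + 0.09) = 0.526 and VTR is 0.10 + 0.10 × 0.474 × 0.5 = 12.4%.

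**7. The X(t) route.** X = V + (1−V)q, so V = (X−q)/(1−q). For V = 0.20, Ab = 0.2 and Pn = 0: X = 0.36 and (0.36−0.20)/0.80 = 0.20. There is no bias, because X(t) covers all infants.

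**The case against.** The strongest reply is that the SAP never says the child scores are summed. Appendix 5 recovers V from X(t), which step 7 shows to be sound, and Section 7.7 describes a single integrated analysis. An integrated likelihood that held the infants' PCR/IgM results would not have this fault. That limits the point to the child-level scores. It does not remove it: Section 10.2 commits to those scores, and no such likelihood for the infants is written down.

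A second reply is that Section 5.2 expects maternal antibody to be gone, as a rule, within 15 months, while Section 3.1 gives two years of follow-up. Ab = 0.2 at the last visit would then mean many infants last seen early. This stands: the bias is small for infants followed long enough where post-natal infection is rare.

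A reader might infer that infections are counted twice and that VTR is always over-estimated. The document does not support that. Each infant receives one score, and the falling-titer rule in the same appendix pulls the other way, so that the bias is downward when f exceeds s. Nor is the literal closed form uniformly upward: at V = 20%, s = 0.7 and f = 0 it gives 0.14 + 0.06 × 0.5 = 17.0% at Ab = 0.

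A reader might also infer that swapping V for the rate among PCR/IgM-negative infants, V(1−s)/(V(1−s) + 1−V), settles the matter. It does so only at f = 0. In the example it gives 0.14 + 0.14 × 0.273 = 17.8% at f = 0.5.

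**Conclusion.** The rule is wrong as written. The probability for infants still IgG+ at last follow-up uses a prior for one population in another, and conditions on only part of the results that define the group. Correcting the closed form alone leaves this in place.

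If the scores enter the VTR analysis, the bias is about V(1−p)(s−f), upward or downward: 26.2% to 18.2% around a true 20% in the example, and 14.7% to 32.0% over the wider assumed range. These figures rest on assumed V, s, Ab and f, no post-natal infection, and scores that are averaged or used as outcomes. The direction cannot be settled from the document. The estimate of V from X(t) is not affected.

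**What to change.** Replace the stand-alone formula in Appendix 5 by one joint likelihood for the newborn PCR/IgM result, the IgG course (with the falling-titer rule) and post-natal infection Pn(t). Estimate V and the child-level probabilities from it together, with priors for newborn-test sensitivity from ZIKA-VID. Use V as the prior only for infants with no informative PCR/IgM or titer result. Correct the printed closed form in the same edit, and let Section 5.2 and Section 10.2, item 1, refer to the new text. State in Section 7.1 how the child-level probabilities enter.

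The cost is SAP wording, one or two more parameters with priors, and slightly wider intervals.

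### The last line of Appendix 5, the probability that an IgG+ child is congenitally infected, does not follow from its own Bayes rule: V cancels, the direction is reversed and post-natal infection is missing

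*SAP*

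**What the plan says.** Appendix 5 first settles most children. PCR, IgM or an agreed syndrome definition makes a child congenitally infected (CI). Loss of IgG, or a consistently falling titer, makes a child not CI. For those still IgG+ when last seen it says "They have a probability of being congenitally infected that increases with time", and adds that "it is necessary to take into account that they may have acquired antibody following a post-natal infection".

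It defines "the probability Ab(t) that an uninfected child born to an antibody +ve mother remains IgG+ t weeks after delivery" and "the probability Pn(t) that an initially IgG- newborn is IgG+ t weeks after birth as a result of a postnatal infection". From these it builds X(t), the proportion IgG+ at time t among babies of women infected in pregnancy. Collecting terms, `X(t) = V + (1-V)Ab(t) + (1-V)(1-Ab(t))Pn(t)`. Without post-natal infection, "we should observe X(t) fall off to an asymptote V representing the vertical transmission rate".

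It then states that "the probability that a child who is IgG+ at age t is CI is" given by Bayes' rule, written correctly in general form, and evaluates it as `V/(V+(1-Ab(t))V)`.

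Two other places rely on this. Section 5.2 (Numerator for VTR) refers to Appendix 5 for the probability of vertical infection in IgG+ infants of unresolved status. Section 10.2, item 1, gives every child a value "which will be 0,1, or a probability determined by the duration of antibody persistence when last tested".

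**The concern.** A posterior probability of infection that does not depend on the prior V cannot come from the Bayes line above it. The non-CI term of the printed expression has three faults:

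- V stands where p(not CI) = 1-V belongs.
- 1-Ab(t), the chance that an uninfected child has lost maternal antibody, stands where Ab(t) belongs.
- Pn(t) is missing, although the same appendix says post-natal infection must be allowed for and includes it in X(t).

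If coded as printed, an undetermined infant last seen soon after birth would be scored as almost certainly infected. One still IgG+ after maternal antibody had gone, which is the stronger evidence of infection, would score one half. The vertical transmission rate is one of the two fundamental outcomes named in Section 10.4, so the per-child infection status needs a correct formula.

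**Working it through.** **Inputs.** V, Ab(t), Pn(t) and X(t) are as defined in Appendix 5. The SAP gives no numerical values, so every value of V, Ab and Pn below is an assumption. The algebra does not depend on them.

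**1. The printed line.** `V/(V+(1-Ab)V) = V/(V(2-Ab)) = 1/(2-Ab)`. V cancels. At Ab = 1 (birth) this is 1; at Ab = 0 it is 0.5.

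**2. Bayes' rule with the appendix's own terms.** X(t) implies p(IgG+ | CI) = 1 and p(IgG+ | not CI) = Ab+(1-Ab)Pn. With p(CI) = V and p(not CI) = 1-V:

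`p(CI | IgG+ at t) = V / {V + (1-V)[Ab + (1-Ab)Pn]} = V / X(t)`

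**3. Comparison with Pn = 0.**

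| Ab(t) | 1 | 0.75 | 0.5 | 0.25 | 0.1 | 0 |
|---|---|---|---|---|---|---|
| Printed, any V | 1.000 | 0.800 | 0.667 | 0.571 | 0.526 | 0.500 |
| Bayes, V = 0.05 | 0.050 | 0.066 | 0.095 | 0.174 | 0.345 | 1.000 |
| Bayes, V = 0.10 | 0.100 | 0.129 | 0.182 | 0.308 | 0.526 | 1.000 |
| Bayes, V = 0.30 | 0.300 | 0.364 | 0.462 | 0.632 | 0.811 | 1.000 |

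**4. Role of Pn(t) once maternal antibody has gone (Ab = 0).** Bayes gives V/(V+(1-V)Pn):

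| Pn(t) | 0 | 0.02 | 0.05 | 0.10 | 0.20 |
|---|---|---|---|---|---|
| V = 0.05 | 1.000 | 0.725 | 0.513 | 0.345 | 0.208 |
| V = 0.10 | 1.000 | 0.847 | 0.690 | 0.526 | 0.357 |
| V = 0.30 | 1.000 | 0.955 | 0.896 | 0.811 | 0.682 |

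The printed line gives 0.500 throughout. Undoing a V/Ab swap gives `V/(V+(1-V)Ab)`, which is 1.000 throughout. Neither responds to Pn.

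**5. The children to whom the formula is applied.** They are those left after identified cases and falling titers have been removed. Let s be the proportion of CI infants already identified by PCR, IgM or syndrome. The CI term becomes V(1-s). With V = 0.20, s = 0.5, Ab = 0.9, Pn = 0 and no one yet removed for a falling titer: 0.10/(0.10+0.80×0.9) = 0.10/0.82 = 0.12. V/X(t) gives 0.20/(0.20+0.72) = 0.22, and the printed line gives 1/1.1 = 0.91.

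**6. Conditional effect on the transmission rate.** Suppose the per-child probabilities were summed into the numerator and a share f of infants were undetermined and IgG+ when last seen. Taking s = 0, the shift is f × [1/(2-Ab) - V/X]. With f = 0.20:

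- Ab = 0.9, Pn = 0: V = 0.05 gives 0.20×(0.909-0.055) = +0.171; V = 0.20 gives 0.20×(0.909-0.217) = +0.138; V = 0.30 gives 0.20×(0.909-0.323) = +0.117.
- Ab = 0, Pn = 0.05: V = 0.20 gives 0.20×(0.500-0.833) = -0.067; V = 0.30 gives 0.20×(0.500-0.896) = -0.079. V = 0.05 is not possible here, because X = 0.05+0.95×0.05 = 0.0975 is below f.

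The shift is proportional to f, so at f = 0.10 each figure halves.

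**The case against.** The best defence is that this is a slip. `(1-Ab(t))V` is `(1-V)Ab(t)` with the symbols exchanged, and the right product appears in X(t) a few lines earlier. Undoing the exchange restores V and the direction. That is probably what happened, and a typesetting or conversion fault cannot be wholly excluded, although the printed line is well formed. Neither explanation supplies Pn(t), so the line needs correcting on any reading.

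Three stronger readings are tempting and are not supported.

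- **That the estimated transmission rate will be biased by a stated amount.** Appendix 5 recovers V from X(t), which is correct. Section 7.1 models a 0/1 outcome, and Appendix 5 says only that its analyses can be integrated there. No section says that the per-child probabilities are summed into the numerator, though Sections 5.2 and 10.2 do assign them.
- **That all infants lost early would count as infected.** Those with PCR, IgM or syndrome evidence are already scored 1, and those with falling titers 0. Only the remainder is affected.
- **That the correct probability must always rise with age.** It rises while loss of maternal antibody dominates. Once Ab(t) is near 0 it falls as Pn(t) grows (step 4). The text's claim of an increase needs that qualification too.

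**Conclusion.** The formula is wrong as written and nothing elsewhere in the SAP repairs it. The cancellation of V, the fall from 1 to 0.5 and the absence of Pn(t) are algebraic facts that hold for any inputs. For an individual child the error is large: 1.00 against 0.05 to 0.30 at birth for V from 0.05 to 0.30, and, with Pn = 0, 0.50 against 1.00 after maternal antibody has gone.

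The damage is confined to the probabilities assigned to undetermined IgG+ infants. Estimation of V through X(t) stands. An effect on the transmission rate arises only if those probabilities are carried into the numerator. With 20% of infants affected it then ranges from about -8 to +17 percentage points over the values in step 6, all of them assumed. It is an illustration, not a forecast.

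Simply substituting V/X(t) would also be inexact for these children, because some infected infants have already been removed from the group.

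**What to change.** 1. For all IgG+ children of infected mothers, replace the last line of Appendix 5 with `V/X(t) = V/{V+(1-V)[Ab(t)+(1-Ab(t))Pn(t)]}`.
2. For the remaining undetermined children use `V(1-s)/{V(1-s)+(1-V)[Ab_r(t)+(1-Ab(t))Pn(t)]}`. Here s is the proportion of CI infants already identified by PCR, IgM or syndrome, and `Ab_r(t)` is Ab(t) restricted to uninfected children not already classified by a falling titer. State how s and `Ab_r(t)` will be estimated, and that infected children are assumed to stay IgG+, as X(t) implies.
3. In the Section 7.1 model use the matching likelihood contribution for these children, `v_i(1-s)+(1-v_i)[Ab_r(t)+(1-Ab(t))Pn(t)]`, and say whether the per-child probabilities are used anywhere else.
4. Reword the text to say that the probability rises while maternal antibody loss dominates and can later fall as Pn(t) grows.
5. Check any code already written against the corrected line. Show any effect on the transmission rate only as a range with its assumptions labelled.

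The cost is a short SAP amendment and a code check. The algebraic correction needs no new data. The version for undetermined children needs s and `Ab_r(t)` to be estimated or given priors.
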